Dose 3 unexposed	 As of the index date, receipt of 2 doses in a primary series of Pfizer-BioNTech original monovalent COVID-19 Vaccine, with no receipt of a third dose of any COVID-19 vaccine Individually matched to individuals in the dose 3 exposed cohort (in at least a ratio of 1:1) on time-specific propensity score (which is described in Section 8.7.2.3.1), age, sex, state of residence (if feasible, or broader geographic region if not feasible), calendar time, and time since receipt of dose 2 	Randomly selected date in a period within close temporal proximity to the date of receipt of dose 3 in corresponding exposed individuals (e.g., within the same calendar month)	Record of any COVID- 19 vaccine other than Pfizer-BioNTech original monovalent COVID-19 Vaccine before the index date

COVID-19 = coronavirus disease 2019.

Individuals who receive 3 doses of the Pfizer-BioNTech original monovalent COVID-19 Vaccine can contribute non-overlapping person-time to both the dose 3 exposed and dose 3 unexposed cohorts. Individuals in the dose 3 unexposed cohort may also contribute persontime to the dose 3 exposed cohort if they subsequently receive a third dose of the Pfizer-BioNTech original monovalent COVID-19 Vaccine more than 2 months after the second dose. Conversely, individuals in the dose 3 cohort may be eligible for inclusion in the dose 3 unexposed cohort before they receive a third dose of Pfizer-BioNTech original monovalent COVID-19 Vaccine.

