Eligibility criteria for third dose analyses of general safety events, spontaneous abortion, stillbirth, and preterm birth in pregnant women are described in Table 5. To be eligible, women must have received 2 doses of the Pfizer-BioNTech original monovalent COVID-19 Vaccine. They must be pregnant for at least 1 day after dose 2 and be continuously enrolled in their health plan from 12 months before the index date (as defined in Table 5) until the end of pregnancy. Depending on whether data on vaccine dose number are recorded in the data sources, additional enrollment may be required from the beginning of authorization of the Pfizer-BioNTech original monovalent COVID-19 Vaccine (i.e., 11 December 2020) to enable dose number identification. The feasibility of determining dose number based on vaccine codes will be confirmed during the monitoring phase of the study, and all eligibility criteria will be fully documented in the SAP.

PFIZER CONFIDENTIAL

CT24-WI-GL02-RF02 3.0 Non-Interventional Study Protocol Template For Secondary Data Collection Study 20-May-2021 Page 58 of 120 The same exposure windows and eligible populations will be used as for the analysis of the doses in the primary series (as defined in Table 3). Only third doses of Pfizer-BioNTech original monovalent COVID-19 Vaccine (received as an additional dose in a primary series or as a booster dose) administered during the exposure windows and more than 2 months after the second dose will be considered for inclusion in the dose 3 exposed cohort. Women who receive a third dose after their pregnancy ends will not contribute person-time to the dose 3 exposed cohort but may contribute unexposed person-time to the dose 3 unexposed cohort.

Table 5.	Cohort definitions for third dose analyses of general safety events ^a ,
	spontaneous abortion, stillbirth, and preterm birth in pregnant women

Cohort	Inclusion criteria	Index date	Exclusion criteria
General safe	ty events		
Dose 3 exposed	 Receipt of a third dose of Pfizer-BioNTech original monovalent COVID-19 Vaccine (either as an additional dose in a primary series or as a booster dose) during the exposure window, more than 2 months after the second dose Note that the first 2 doses are not required to have been received during the exposure window 	• Date of third dose of Pfizer- BioNTech original monovalent COVID-19 Vaccine	Receipt of any COVID-19 vaccine other than Pfizer- BioNTech original monovalent COVID-19 Vaccine before the index date

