Dose 3 unexposed	 As of the index date, receipt of 2 doses of Pfizer- BioNTech original monovalent COVID-19 Vaccine with no receipt of a third dose of any COVID-19 vaccine Individually matched to women in the third dose– exposed cohort on maternal age, US state (if feasible, otherwise, geographic region), and pregnancy start date 	• Equivalent to the gestational age (in days) at the time of the dose 3 exposed individual's index date	 Receipt of any COVID-19 vaccine other than Pfizer- BioNTech original monovalent COVID-19 Vaccine before the index date Receipt of a third dose of Pfizer-BioNTech monovalent COVID-19 Vaccine on or before the index date
Pregnancy o	utcomes		•
Dose 3 exposed	 Receipt of a third dose of Pfizer-BioNTech original monovalent COVID-19 Vaccine (either as an additional dose in a primary series or as a booster dose) during the exposure window more than 2 months after the second dose. Note that the first 2 doses are required to have been received during the exposure window. 	• Date of third dose	Receipt of any COVID-19 vaccine other than Pfizer- BioNTech original monovalent COVID-19 Vaccine before the index date

	i birtir in pregnant women		
Cohort	Inclusion criteria	Index date	Exclusion criteria
Dose 3 unexposed	 No receipt of a third dose of Pfizer-BioNTech original monovalent COVID-19 Vaccine (either as an additional dose in a primary series or as a booster dose) during the exposure window, as of more than 2 months after the second dose Note that the first 2 doses are required to have been received during the exposure window Individually matched to women in the third dose– exposed cohort on maternal age, estimated pregnancy start, US state (if feasible; otherwise, geographic region), and time since second dose 	• Equivalent to the gestational age (in days) at the time of the dose 3 exposed individual's index date	 Receipt of any COVID-19 vaccine other than Pfizer- BioNTech original monovalent COVID-19 Vaccine before the index date Receipt of a third dose of COVID-19 vaccine during the exposure window, on or before the index date
COLUD 10			

Table 5.Cohort definitions for third dose analyses of general safety eventsa,
spontaneous abortion, stillbirth, and preterm birth in pregnant women

COVID-19 = coronavirus disease 2019.

a. Safety events of interest listed in Table 8 in Section 8.3.2.1.

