In pregnant women who have received 2 doses in a primary series of Pfizer-BioNTech original monovalent COVID-19 Vaccine, the risk of general safety events, spontaneous abortion, stillbirth, and preterm birth will be compared among women who have received a third dose (either as an additional dose in a primary series or as a booster dose) more than 2 months after the second dose versus that among women who have not received a third dose of any COVID-19 vaccine. To minimize confounding by seasonality and maternal age, within the data from each data research partner, pregnant women in the dose 3 exposed cohort will be matched to women in the dose 3 unexposed cohort on estimated pregnancy start date (+/- 14 days), state (if feasible, or broader geographic region if not feasible), maternal age, and time since receipt of dose 2. Propensity score estimation will be conducted following a similar process as that for the primary series analysis of general safety events, spontaneous abortion, stillbirth, and preterm birth in pregnant women (as described in Section 8.7.2.3.2.1). As with the primary series analysis, propensity scores will be estimated within the matched population of dose 3 exposed and dose 3 unexposed individuals and incorporated into regression analysis for exposure-outcome associations (e.g., through weighting or stratification) to address confounding by other variables. The matching and propensity score estimation process will be conducted first for the overall population of pregnant women. The process will then be repeated for the subsets of pregnant women eligible for analyses of the different safety events of interest (e.g., pregnancies surviving beyond 20 completed weeks of pregnancy for analysis of stillbirth; live births for analysis of

PFIZER CONFIDENTIAL

CT24-WI-GL02-RF02 3.0 Non-Interventional Study Protocol Template For Secondary Data Collection Study 20-May-2021 Page 95 of 120 preterm birth and small size for gestational age; and live births that can be linked to infants for analysis of major congenital malformations). Further details on the matching process and estimation of propensity scores will be described in the SAP.

8.7.2.3.2.3. Analysis of birth outcomes following receipt of at least 1 dose in pregnant women

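### For general safety events after a third dose in pregnancy, Table 5 and Section 8.7.2.3.2.2 give different matching sets; only the latter matches on time since dose 2

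*Protocol*

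**What the plan says.** Section 8.2.3.2 names Table 5 as the place where eligibility for the third-dose analyses in pregnant women is described. It limits the exposed group to third doses "administered during the exposure windows and more than 2 months after the second dose will be considered for inclusion in the dose 3 exposed cohort".

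For general safety events, the Table 5 comparator must meet this condition: "As of the index date, receipt of 2 doses of Pfizer- BioNTech original monovalent COVID-19 Vaccine with no receipt of a third dose". She is then matched to the third-dose "exposed cohort on maternal age, US state (if feasible, otherwise, geographic region), and pregnancy start date". The only other timing condition tied to dose 2 is in the section text: "They must be pregnant for at least 1 day after dose 2".

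Three other places include time since dose 2:

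- The pregnancy-outcomes comparator row of the same Table 5 ends its matching list with "geographic region), and time since second dose". It also refers to a point more than 2 months after dose 2.
- Table 2 (Section 8.2.2.2), the third-dose analysis outside pregnancy, ends its list with "calendar time, and time since receipt of dose 2".
- Section 8.7.2.3.2.2 on confounding control states that "the risk of general safety events, spontaneous abortion, stillbirth, and preterm birth will be compared among women who have received a third dose". For that analysis it matches on pregnancy start (within 14 days) and on "state (if feasible, or broader geographic region if not feasible), maternal age, and time since receipt of dose 2".

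**The concern.** The two texts describe one analysis, the one that serves secondary objective 6 (relative risk of safety events, including myocarditis/pericarditis, after a third dose in pregnant women). They differ on a factor that determines who may be a comparator. Because the two comparator rows of Table 5 also differ from each other, a programmer working from the table could take the omission as intended.

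The factor matters because the exposed are held more than 2 months away from dose 2 and, under Table 5 alone, the comparators are not. Section 6 quotes labelling that places the myocarditis and pericarditis risk particularly in the 7 days after the second dose. Comparator time taken soon after dose 2 would carry that excess and exposed time would not. In a safety study, this error runs toward reassurance.

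**Working it through.** **Plan's own figure.** The protocol gives no precision or effect figure for this analysis. The nearest is the 92% in Section 8.5, which concerns the primary series. It reproduces:

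- Expected comparator cases = 5,000,000 × 2 doses × 21/365.25 × 10/100,000 = 57.5; exposed cases = 1.4 × 57.5 = 80.5.
- SE of log RR = √(1/57.5 + 1/80.5) = 0.173.
- Φ((ln(2.5/1.4) − 1.96 × 0.173)/0.173) = 0.919.

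This confirms how the 21-day window is used. The point does not rest on it.

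**Overlap with dose 2's window, Table 5 read alone.** Let W be the risk window in days (Table 8: 21 for myocarditis/pericarditis, 28 or 42 for most others) and d the days from dose 2 to the comparator's index date. Her follow-up covers days d+1 to d+W after dose 2; dose 2's window covers days 1 to W. Overlap = max(0, W − d).

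| d | W = 21 | W = 28 | W = 42 |
|---|---|---|---|
| 1 | 20 (95%) | 27 (96%) | 41 (98%) |
| 7 | 14 (67%) | 21 (75%) | 35 (83%) |
| 14 | 7 (33%) | 14 (50%) | 28 (67%) |
| 61 | 0 | 0 | 0 |

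**Overlap with matching on time since dose 2.** The comparator sits about as far from dose 2 as her exposed match, so d is above roughly 61 days and overlap is zero for windows up to 42 days. No matching tolerance is stated, but a comparator would have to be more than 61 − 42 = 19 days closer to dose 2 than her match before a 42-day window overlapped, and more than 61 − 21 = 40 days closer for a 21-day window. For the 180-day and 365-day windows, overlap remains (119 and 304 days at d = 61) but is about equal in both groups.

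**Effect on the estimate if Table 5 alone is used.** Let f be the share of comparator person-time inside dose 2's window, and RR2 and RR3 the true rate ratios after doses 2 and 3. Exposed time is free of dose 2's window for W up to 42, so observed RR = RR3 / (1 + f(RR2 − 1)).

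The documents give neither f nor a rate ratio in pregnancy. Section 6 gives 2.4 (95% CI 0.4–24.9) for this vaccine, in the 7 days after vaccination at ages 12 to 39. It is used here only as an assumption, with 1.4 and 5 to show a range, and RR2 is set equal to RR3:

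| f | both 1.4 | both 2.4 | both 5 |
|---|---|---|---|
| 5% | 1.37 | 2.24 | 4.17 |
| 10% | 1.35 | 2.11 | 3.57 |
| 25% | 1.27 | 1.78 | 2.50 |
| 50% | 1.17 | 1.41 | 1.67 |
| 95% | 1.01 | 1.03 | 1.04 |

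The observed ratio falls below 1 when f(RR2 − 1) exceeds RR3 − 1. With RR3 = 1.4 and RR2 = 2.4 this needs f above 0.4/1.4 = 29%; at f = 50% the result is 1.4/1.7 = 0.82. If RR2 = 1 there is no bias.

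**The case against.** The strongest reply is that the protocol already prescribes the right match. Section 8.7.2.3.2.2 names general safety events in pregnant women and says the groups will be matched on time since dose 2, and the remaining detail goes to the SAP. This largely stands: under that section the overlap disappears for every window up to 42 days. It does not remove the contradiction. Table 5 is named as the source of eligibility, states a shorter matching list, and the protocol gives no order of precedence. Two conflicting lists are not a detail deferred to the SAP.

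A reader might infer more than the documents support, in three ways:

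- **That the design as a whole admits comparators given dose 2 the day before, and so hides a booster risk.** Only one table row allows this; the section on confounding control excludes it.
- **That the bias is very large.** Section 6 reports 12.6 cases per million second doses in 21 days. Table 9's background of 1 to 10 per 100,000 person-years is 0.57 to 5.75 per million per 21 days, so the ratio is 2.2 to 22. With 20% of comparators affected, a true ratio of 2.0 could then be read as 2.0/(1 + 0.2 × 20.9) = 0.39. But the 12.6 is for any mRNA vaccine in both sexes at ages 12 to 39, the background is for the general population, the 20% is assumed, and the sum gives every affected comparator all 21 days of overlap. The product-specific 2.4 lies near the low end.
- **That a separate 2-month minimum for comparators already stands in Table 2 and Section 8.7.2.3.2.2.** Neither has one. Only the pregnancy-outcomes row of Table 5 uses such wording.

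**Conclusion.** The point holds as an internal contradiction with a known direction of harm if it is resolved the wrong way. One analysis has two matching sets, and the Table 5 version lets comparators fall inside dose 2's own risk window. For any event that dose 2 raises, that biases the dose 3 relative risk toward or below 1.

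The size cannot be fixed from the documents. The illustration of 2.4 read as 2.11 (10% of comparator time) or 1.78 (25%) assumes equal rate ratios after both doses, a constant excess across the window, and a figure that is neither specific to dose 2 nor to pregnancy. Its interval alone, at 10% of comparator time, moves the multiplier on the true ratio from 1/(1 − 0.06) = 1.06 to 1/(1 + 2.39) = 0.29. If Section 8.7.2.3.2.2 is followed, the bias is about nil for windows up to 42 days. The texts should be reconciled before matching for the final analysis is run.

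**What to change.** In Table 5, general safety events, dose 3 unexposed, add time since dose 2 to the matching factors. The row then agrees with Section 8.7.2.3.2.2, with Table 2 and with the pregnancy-outcomes row of the same table.

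Optionally, also require that the comparator's index date be more than 2 months after dose 2. This mirrors the condition on the exposed and the wording of the pregnancy-outcomes row. It is largely redundant once matching is in place, but it guards against a wide matching tolerance.

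The cost is one line in the table and a matching step already planned for the other third-dose cohorts. The downside is somewhat fewer eligible matches, in an analysis that Section 8.9 already expects may be small.

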7. RESEARCH QUESTION AND OBJECTIVES

Research questions

Among the general population, immunocompromised individuals, pregnant women, and individuals with a history of COVID-19:

- 1. What is the incidence of safety events of interest, including myocarditis/pericarditis, among individuals receiving at least 1 dose in a primary series¹ of Pfizer-BioNTech original monovalent COVID-19 Vaccine compared with that among individuals who have not received any vaccination for COVID-19 in the US?
- 2. In individuals aged 5 years and older who have received the first and second dose in a primary series¹ of Pfizer-BioNTech original monovalent COVID-19 Vaccine, what is the incidence of safety events of interest, including myocarditis/pericarditis, among individuals vaccinated with a third dose (either as an additional dose in a primary series or as a booster dose) of Pfizer-BioNTech original monovalent COVID-19 Vaccine compared with that among individuals who have not received a third dose of any COVID-19 vaccine in the US?
- 3. What is the prevalence of birth outcomes of interest (including major congenital malformations and small size for gestational age) in infants born to pregnant women who were exposed to Pfizer-BioNTech original monovalent COVID-19 Vaccine as compared with that among infants born to pregnant women who were not exposed to any COVID-19 vaccine in the US?

Primary study objectives

Among the overall study population and subgroups of pregnant women, immunocompromised individuals, and individuals with a history of COVID-19:

- 1. In individuals aged 5 years and older: To estimate the RR of safety events of interest (including myocarditis/pericarditis) following receipt of a first, second, or third (if received within 2 months of the second dose) dose in a primary series¹ of Pfizer-BioNTech original monovalent COVID-19 Vaccine compared with that among individuals with no receipt of any COVID-19 vaccine
- 2. In individuals aged 6 months through 4 years: To estimate the RR of safety events of interest (including myocarditis/pericarditis) following receipt of a first, second, or third dose in a primary series¹ of Pfizer-BioNTech original monovalent COVID-19 Vaccine compared that among individuals with no receipt of any COVID-19 vaccine

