- 3. In individuals aged 5 years and older who have received 2 doses in a primary series¹ of Pfizer-BioNTech original monovalent COVID-19 Vaccine: To estimate the RR of safety events of interest (including myocarditis/pericarditis) following a third dose (as an additional dose in a primary series¹ or as a booster dose) of Pfizer-BioNTech original monovalent COVID-19 Vaccine received more than 2 months after the second dose compared with that among individuals without a third dose of any COVID-19 vaccine

Among pregnant women:

4. To estimate the birth prevalence and prevalence ratio of birth outcomes among infants born to pregnant women vaccinated with Pfizer-BioNTech original monovalent COVID-19 Vaccine compared with that among infants born to unvaccinated pregnant women.

Secondary objectives:

Among the overall study population and subgroups of pregnant women, immunocompromised individuals, and individuals with a history of COVID-19:

- 1. To describe the proportion of individuals receiving Pfizer-BioNTech original monovalent COVID-19 Vaccine, stratified by number of doses
- 2. To describe—among individuals who have received a first dose of Pfizer-BioNTech original monovalent COVID-19 Vaccine—the timing and type of second dose of COVID-19 vaccine (Pfizer-BioNTech original monovalent COVID-19 Vaccine or other COVID-19 vaccine)

- 3. To describe baseline characteristics (demographics and comorbidities) of individuals who have received at least 1 dose of Pfizer-BioNTech original monovalent COVID-19 Vaccine and those with no record of COVID-19 vaccination of any type
- 4. To describe—among individuals who have received 2 doses of Pfizer-BioNTech original monovalent COVID-19 Vaccine—the timing and type of a third dose of COVID-19 vaccine (Pfizer-BioNTech original monovalent COVID-19 Vaccine or other COVID-19 vaccine)
- 5. To describe—among individuals aged 5 years and older who have received at least 2 doses in a primary series¹ of Pfizer-BioNTech original monovalent COVID-19 Vaccine—baseline characteristics (demographics and comorbidities) of individuals who received a third dose (either as an additional dose in a primary series¹ or as a booster dose) of Pfizer-BioNTech original monovalent COVID-19 Vaccine more than 2 months after the second dose and those with no record of a third dose of COVID-19 vaccination of any type

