Dose 3 exposed	 Record of a third dose (either as an additional dose in a primary series or as a booster dose) of Pfizer-BioNTech original monovalent COVID-19 Vaccine during the exposure window For analyses of general safety events, the first and second dose are not required to have been administered during the exposure window For analyses of spontaneous abortion, stillbirth, and preterm birth, the first and/or second doses may be administered before the exposure window but only the third dose will be eligible for the dose 3 cohort 	Date of third dose	Record of any COVID-19 vaccine other than Pfizer- BioNTech original monovalent COVID-19 Vaccine before the index date (or during the exposure window before the index date in analyses of spontaneous abortion, stillbirth, and preterm birth)
Dose 1 unexposed	 No record of any COVID-19 vaccine as of the index date (or no record of any COVID-19 vaccine during the exposure window before the index date in analyses of spontaneous abortion, stillbirth, and preterm birth) Individually matched to women in dose 1 cohort on maternal age and pregnancy start date and US state (if feasible) 	Equivalent of the gestational age (in days) at the time of the of the dose 1 exposed individual's index datec	Record of any COVID-19 vaccine as of the index date (or during the exposure window before the index date in analyses of spontaneous abortion, stillbirth, and preterm birth)
Dose 2 unexposed	Same criteria as the dose 1 unexposed cohort, but matched individually to women in the dose 2 exposed cohort	Equivalent of the gestational age (in days) at the time of the dose 2 exposed individual's index date ^c	Same criteria as those for the dose 1 unexposed cohort

Table 4.	Cohort definitions for primary series analyses of general safety events,
	spontaneous abortion, stillbirth, and preterm birth in pregnant women ^a

Cohort	Inclusion criteria	Index date	Exclusion criteria
Dose 3 unexposed	Same criteria as those for the dose 1 unexposed cohort, but matched individually to women in the dose 3 exposed cohort	Equivalent of the gestational age (in days) at the time of the dose 3 exposed individual's index date ^c	Same criteria as those for the dose 1 unexposed cohort

COVID-19 = coronavirus disease 2019; FU = follow-up.

a. Safety events of interest listed in Table 8 in Section 8.3.2.1.

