Note: Individuals who receive 3 doses of the vaccine can contribute person-time to both the dose 3 exposed and dose 3 unexposed cohorts. Individuals in the dose 3 unexposed cohort may contribute person-time to the dose 3 exposed cohort if they subsequently receive a third dose of the Pfizer-BioNTech original monovalent COVID-19 Vaccine. Conversely, individuals in the dose 3 exposed cohort may be eligible for the dose 3 unexposed cohort before they receive a third dose of Pfizer-BioNTech original monovalent COVID-19 Vaccine.

8.2.3.3. Analysis of small size for gestational age and major congenital malformations in pregnant women

Cohort definitions for analyses of small size for gestational age and major congenital malformations in pregnant women are presented in Table 6. For these analyses, separate cohorts of the following will be formed: (1) pregnant women exposed to at least a first, second, or third dose of Pfizer-BioNTech original monovalent COVID-19 Vaccine during the exposure window (as defined in Table 3) and (2) pregnant women not exposed to any COVID-19 vaccine during the exposure window (as defined in Table 3).

Table 6.Cohort definitions for analysis of small size for gestational age and major
congenital malformations in pregnant women

Cohort	Inclusion criteria	Index date	Exclusion criteria
Exposed	Record of at least a first, second, or third dose (as an additional dose in a primary series or as a booster dose) of Pfizer-BioNTech original monovalent COVID-19 Vaccine during the exposure window (as defined in Table 3)	Estimated pregnancy start	Record of another brand of COVID-19 vaccine other than Pfizer-BioNTech original monovalent COVID-19 Vaccine during the exposure window No record of Pfizer- BioNTech original monovalent COVID-19 Vaccine during the exposure window
Unexposed	No record of any COVID-19 vaccine during the exposure window (as defined in Table 3), individually matched to women in the exposed cohort on maternal age and pregnancy start	Estimated pregnancy start	Record of any COVID-19 vaccine during the exposure window

COVID-19 = coronavirus disease 2019.

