 - Asthma
 - Liver disease

PFIZER CONFIDENTIAL

CT24-WI-GL02-RF02 3.0 Non-Interventional Study Protocol Template For Secondary Data Collection Study 20-May-2021 Page 74 of 120

- Kidney disease
- Cancer
- Obesity, identified in the 12 months before the index date, with proxies based on diagnosis and procedure codes (capture anticipated to be incomplete since documentation via diagnosis or procedure codes is not routinely done in claims data)
- Alcohol use, identified in the 12 months before the index date, with proxies based on diagnosis and procedure codes (capture anticipated to be incomplete)
- Smoking, identified in the 12 months before the index date, with proxies based on diagnosis and procedure codes (capture anticipated to be incomplete)
- Multiple pregnancy, identified during pregnancy via diagnosis codes. Information recorded after the index date will be used to identify potential confounders
- Gestational diabetes, identified during pregnancy via diagnosis codes
- Preeclampsia/eclampsia, identified during pregnancy via diagnosis codes
- Gestational hypertension
- TORCH infections (toxoplasmosis, other [syphilis, varicella-zoster, parvovirus B19], rubella, cytomegalovirus, and herpes infections), identified during pregnancy via diagnosis codes
- Teratogenic medications from 28 days before pregnancy up to and including the end of pregnancy, identified via pharmacy dispensing and procedure codes
- Vaccinations other than COVID-19 vaccinations (including those administered concomitantly with Pfizer-BioNTech original monovalent COVID-19 Vaccine) from 28 days before pregnancy up to and including the end of pregnancy, identified via pharmacy dispensing and procedure codes

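### For birth outcomes and primary-series pregnancy outcomes, comparators need only be undosed within the exposure window, so previously vaccinated women can count as unexposed, against the stated objectives and without adjustment for prior COVID-19 vaccination

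*Protocol*

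**What the plan says.** **Objectives.** In Protocol Section 7, primary objective 4 sets the prevalence of birth outcomes after vaccination "compared with that among infants born to unvaccinated pregnant women". Objective 1, which also covers the subgroup of pregnant women, uses the comparator of no receipt of any COVID-19 vaccine (objective 2 in the same section is worded alike: "compared with that among individuals with no receipt of any COVID-19 vaccine").

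**Birth outcomes.** Table 6 in Section 8.2.3.3 admits an unexposed woman with "No record of any COVID-19 vaccine during the exposure window" and excludes her only for a "record of any COVID-19 vaccine during the exposure window". Sections 8.1 and 8.7.2.3.2.3 repeat the window-only contrast.

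**Pregnancy outcomes.** Table 4 in Section 8.2.3.1 has two rules in the same cell. General safety events require "No record of any COVID-19 vaccine as of the index date". The other outcomes require "no record of any COVID-19 vaccine during the exposure window before the index date in analyses of spontaneous abortion, stillbirth, and preterm birth".

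**Window.** Table 3 opens it 4 weeks before estimated pregnancy start for every outcome. For malformations it closes at 13-6/7 weeks. Section 8.2.3 lets women vaccinated outside the window contribute unexposed person-time. Its example is vaccination after birth, but it sets no limit on earlier doses.

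**Confounding control.** Matching is on maternal age, estimated pregnancy start and, in Sections 8.7.2.3.2.1 and 8.7.2.3.2.3, state or region. The vaccination covariate for pregnancy safety outcomes in Section 8.3.3.1 is "Vaccinations other than COVID-19 vaccinations".

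**The concern.** The objectives promise a comparison with unvaccinated women. The cohort tables deliver a comparison with women not vaccinated in a particular window. A woman who finished two doses and a booster five weeks before conception meets the Table 6 definition of unexposed. For malformations, so does a woman first vaccinated in the second trimester.

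The exposed side is mixed too. Table 6 pools first, second and third doses. In Table 4, women whose earlier doses precede the window can still enter the exposed cohorts through a later dose: the dose 2 row places such a woman in the dose 2 cohort, while footnote b says her second dose could contribute to the dose 1 cohort. One estimate can therefore combine a booster against previously vaccinated women, a booster against never vaccinated women, and a first dose against either.

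Exposures accrue from 11 December 2020 to 18 April 2023, and Section 6 dates booster authorization from September 2021, so this mix can shift over calendar time. Women already vaccinated before pregnancy may differ from those never vaccinated in health and care-seeking. Section 8.7.3.2 itself recognises healthy-vaccinee effects when it rules out pre-vaccination control periods. Nothing listed for these outcomes controls for that difference directly.

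**Working it through.** No figure in the protocol depends on this point, so the check is a comparison of text, followed by an illustration with assumed inputs.

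**Step 1: comparator by analysis.**

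| Analysis in pregnant women | Comparator rule | Can include women dosed before the window? |
|---|---|---|
| General safety events, primary series (Table 4) | no COVID-19 vaccine as of the index date | No |
| Spontaneous abortion, stillbirth, preterm birth, primary series (Table 4) | no dose in the window before the index date | Yes |
| Small size for gestational age, malformations (Table 6) | no dose in the window | Yes |
| Third dose more than 2 months after the second (Table 5) | two prior doses required in both groups | By design, in both groups |

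The mismatch is confined to the second and third rows.

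**Step 2: is prior vaccination controlled?** In those two rows, neither the matching variables nor the listed covariates include COVID-19 vaccination before the window. The dose-received variable in Section 8.3.3.1 belongs to the general-safety list and most naturally describes the index dose. By contrast, the late third-dose analyses fix two prior doses and match on time since dose 2 (Section 8.7.2.3.2.2).

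**Step 3: possible size.** Let RR be the true ratio against never vaccinated women, p the share of comparators vaccinated before the window, and r their risk relative to never vaccinated women. Taking RR as common to all exposed women,

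observed ratio = RR / (1 − p + p·r).

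The protocol gives neither p nor r for these outcomes. Both are assumptions, as is RR = 1.4.

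| p | r = 1.4 (earlier doses carry the same effect) | r = 1.0 (no difference) | r = 0.8 (previously vaccinated at lower risk) |
|---|---|---|---|
| 0.1 | 1.4/1.04 = 1.35 | 1.40 | 1.4/0.98 = 1.43 |
| 0.3 | 1.4/1.12 = 1.25 | 1.40 | 1.4/0.94 = 1.49 |
| 0.5 | 1.4/1.20 = 1.17 | 1.40 | 1.4/0.90 = 1.56 |
| 0.7 | 1.4/1.28 = 1.09 | 1.40 | 1.4/0.86 = 1.63 |

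At p = 0 the observed ratio equals the true one. Over p = 0.1 to 0.7 and r = 0.8 to 1.4 it runs from 1.09 to 1.63, on either side of 1.40.

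**The case against.** **The window contrast is deliberate.** It appears consistently in Sections 8.1, 8.2.3, 8.2.3.3 and 8.7.2.3.2.3, and Section 8.2.3 gives reasons for where the window opens. Research question 3 speaks of exposed and not exposed women, and the wording of objective 4 could be shorthand. This stands: the contrast is a legitimate estimand. It is not the one the objectives state, and calling it deliberate does not balance prior vaccination between the groups.

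**A never vaccinated contrast is already planned.** Section 8.7.3.3 proposes historical comparators from before COVID-19 vaccines for pregnancy and birth outcomes. Those women cannot have been vaccinated, so comparator-side dilution vanishes. This stands in part. The analysis is conditional on feasibility, serves as a sensitivity analysis, leaves the exposed group mixed, and uses a type of comparator that Section 8.1 rejects for the main design.

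**Details belong in the SAP.** Propensity score and matching details are deferred to it, and other vaccinations are a partial proxy for attitude to vaccination. The SAP could add the covariate. It would still not make the comparators unvaccinated, and the protocol's own list omits it.

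**Stronger readings a reader might infer.** One is that every pregnancy comparator is affected; Table 4 rules this out for general safety events and Table 5 for late third doses. Another is that the ratios are attenuated by a calculable amount; the protocol gives no share of previously vaccinated comparators, and the direction is not fixed. A third is that Section 8.2.3.1, which also requires the Table 2 criteria, removes previously vaccinated women. Table 2 requires two prior doses of its unexposed cohort, so it cannot do so, and it does not govern Table 6.

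**Conclusion.** The point holds for the two birth outcomes in Table 6 and the three primary-series pregnancy outcomes in Table 4. For these, the unexposed definition and the objectives describe different comparators, both groups can mix women with and without earlier doses, and prior COVID-19 vaccination is not controlled.

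The consequence cannot be sized from the protocol. The range of 1.09 to 1.63 for a true 1.4 shows only what the assumed shares and risks would produce. If doses before the window have no effect on the outcome, there is no dilution, and the remaining problem is unadjusted difference between previously and never vaccinated women. If they do have an effect, the estimate is also not the vaccinated-versus-unvaccinated ratio of the objectives. The documents do not support calling the window design invalid or the result biased toward no effect. They do support correcting the mismatch before the analysis, since objective 4 is a primary objective of a study that is a regulatory safety commitment.

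**What to change.** 1. For the Table 6 outcomes and for spontaneous abortion, stillbirth and preterm birth in Table 4, add recorded COVID-19 vaccination before the exposure window to the propensity score: at least yes or no, and number of doses where enrollment allows.
2. Report a sensitivity analysis restricted to women with no recorded dose before the window in either group.
3. If the window contrast stays primary, reword the objectives to say not vaccinated during the exposure window. This also covers women dosed after 13-6/7 weeks in the malformation analysis. Doses after the window are not baseline information and should not enter the propensity score.

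Rewording alone removes the contradiction but not the confounding, so items 1 and 2 are needed as well.

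**Cost.** A yes/no covariate is cheap. A dose count is less so: Section 8.3.1 expects most vaccination codes to lack dose number, counting doses in order needs enrollment from 11 December 2020, and Section 8.2.3 requires only 12 months before the index date. Section 8.9 warns, for third-dose analyses, that such a requirement may exclude many individuals. Capture of earlier doses will be incomplete, so some imbalance will remain. The restricted analysis will have fewer women, more so if longer enrollment is imposed, and it drops exposed women whose earlier doses preceded the window. That is why it is proposed as a sensitivity analysis.
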